2.5 Schematic diagram of study design

3. STUDY POPULATION

3.1 Study Population (base)

Newborn infants born at (near-)term, meaning ≥36+0 weeks of gestation, will be included in the study. Subjects will be recruited from all Dutch NICUs collaborating in the Dutch Neonatal Research Network (NNRN).

3.2 Inclusion criteria

In order to be eligible to participate in this study, a subject must meet all of the following criteria:

- (Near-)Term infants, ≥36+0 weeks of gestation, admitted to one of the Dutch NICUs, diagnosed with PAIS, confirmed by MRI within 7 days after presentation with clinical symptoms.
- PAIS as characterized by a predominantly unilateral ischemic lesion within the territory of the MCA, with involvement of the corticospinal tracts, cortex, white matter and basal ganglia.
- Written informed consent from custodial parent(s).

3.3 Exclusion criteria

A potential subject who meets any of the following criteria will be excluded from participation in this study:

- Any proven or suspected congenital anomaly, chromosomal disorder, metabolic disorder.
- Presence of an infection of the central nervous system.
- No realistic prospect of survival, (e.g. severe brain injury), at the discretion of the attending physician.

3.4 Sample size calculation

We aim to include 10 infants diagnosed with PAIS on MRI, who will be treated with MSCs via the nasal route.

Since this is a proof-of-principle study, the sample size is not only calculated based on expected power, but on the feasibility to be successful in recruitment of individuals needed for this study in order to complete the protocol in 2 years. It is expected that about 180,000 infants will be born alive per year.(StatLine 2015) Since the incidence of PAIS is 1/2300 there will be about 80 PAIS patients in the Netherlands yearly. A study from our group showed that about 26% of all PAIS patients involved the main MCA branch.(Harteman et al. 2012) Based

on this expectation, we think it will be feasible to recruit 10 PAIS patients in 12-24 months. We furthermore expect only a minimal drop out of initially included patients because PAIS is not life-threatening and follow-up is tightly regulated in all NICUs, including the WKZ.

Data analysis

Data will be analyzed on an intention to treat basis. SAEs are planned to be compared. Statistical analysis is described in detail in chapter 8.

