2.2 Duration

The duration of the study for each subject from inclusion until study end will be a maximum of 3 months, comprising a 1 week intervention period and follow-up until 3 months. Subject recruitment will be (approximately) 12-24 months, at the longest, depending on when the intended number of subjects is included. This study is expected to last for approximately 2.5 years, but will only end after all 10 subjects have been included, treated and have been seen for follow-up (MRI and neurodevelopmental testing) at 3 months of age.

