4. TREATMENT OF SUBJECTS

4.1 Investigational product/treatment

The treatment protocol requires that infants will receive MSCs as soon as possible after confirmation of the PAIS, but no later than the end of the first week of onset of presenting clinical symptoms. Steps to be undertaken before MSC administration include:

- A bacterial culture taken from both nostrils before administration of MSCs.
 Blood samples will be collected before administration of MSCs. Blood samples are taken routinely in the hospital for clinical purposes, but some extra material (0.5-1 mL) will be collected to determine infection markers CRP, procalcitonin and complete blood count. These samples will be combined with routine blood sampling and taken from routinely placed (arterial) catheters
- 30 minutes prior to delivery of the cells, the nose will be cleaned with saline using standard procedures operative at the NICU.

After these procedures have been performed, infants will receive one dose of 50 x 10⁶ MSCs intranasally. We will use a sterile plastic (e.g. 1,0 mL) syringe containing the MSCs to slowly drip the MSCs alternatively in both nostrils. Blood samples will be collected again at 24 hours after administration of MSCs.

The syringe with MSC will be packaged at the CT-F of the UMC Utrecht and will be delivered to the NICU by the clinical research nurse.

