6.5 Replacement of individual subjects after withdrawal

Not applicable.

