8. STATISTICAL ANALYSIS

In this study, 10 newborns will be included who will be treated with MSCs via the nasal route. This is a phase I/II, open-label, single-arm, single-center intervention study to assess the safety and feasibility of intranasal BM-MSCs in neonatal stroke patients.

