8.1 Study parameter(s)

Safety is defined primarily as the absence of treatment-related serious adverse events (SAEs) according to the Consolidated Standards of Reporting Trials (chapter 7.2 and bron), secondly as the absence of dose-limiting toxicity, defined as death within 24 hours after MSC transplantation or anaphylactic shock related to the MSC administration, and thirdly as the absence of adverse events at 3 months of age in terms of cerebral damage and neurodevelopmental outcome (see secondary outcome).

For acute safety, all vital signs and blood sample parameters (continuous variables) at baseline and at 24 hours following MSC transplantation will be compared using Wilcoxon signed-rank tests. The occurrence of SAE's, including mortality, toxicity, tumor growth, etc (see chapter 11.1) will be expressed in percentages and analyzed qualitatively.

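### Safety in this single-arm study is put on an intention-to-treat basis, so an infant included but never given MSCs would count in the denominator for treatment-related SAEs

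*Combined protocol and SAP*

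**What the plan says.** Under Data analysis, section 3.4 reads: "Data will be analyzed on an intention to treat basis. SAEs are planned to be compared". It refers to chapter 8 for detail. Chapter 8 describes the design: "This is a phase I/II, open-label, single-arm, single-center intervention study". Section 8.1 then says of SAEs: "The occurrence of SAE's, including mortality, toxicity, tumor growth, etc (see chapter 11.1) will be expressed in percentages and analyzed qualitatively". Neither place defines a treated or safety set, or a denominator for those percentages. Sections 6.1.1 and 8.1 define safety first as the absence of treatment-related SAEs.

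On timing, section 2.4 includes an infant once PAIS is confirmed on MRI and the parents have consented in writing; MSCs are given after inclusion. Section 3.2 requires PAIS to be "confirmed by MRI within 7 days after presentation with clinical symptoms". Section 4.1 sets the latest time for dosing as "no later than the end of the first week of onset of presenting clinical symptoms". Section 6.4 allows withdrawal at any time.

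On numbers, chapter 8 expects that "10 newborns will be included who will be treated with MSCs via the nasal route". Section 2.2 says the study "will only end after all 10 subjects have been included, treated and have been seen for follow-up". Section 6.5, on replacement after withdrawal, says only "Not applicable".

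**The concern.** Intention to treat keeps randomised groups comparable. With one arm it has no such role, and for a safety endpoint it can admit infants who were never exposed. An undosed infant cannot contribute a treatment-related SAE but adds one to the denominator, so the reported percentage falls below the percentage among exposed infants.

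There is also a mixing problem. The percentages in section 8.1 cover SAEs generally, mortality included. A stroke-related SAE in an undosed infant would therefore enter a figure meant to describe experience after MSCs.

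What is at stake is the main safety figure from what the protocol calls the first intranasal use of MSCs in humans. If the denominator is not settled in advance, it will be chosen after the events are known.

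**Working it through.** **The plan's own figure.** The size of 10 rests on recruitment. The supporting arithmetic in section 3.4 reproduces: 180,000 / 2,300 = 78.3 PAIS cases a year, against the stated 80 or so; 78.3 × 0.26 = 20.3 a year with main-branch MCA involvement. No target SAE rate or precision is given, so there is no planned safety percentage to reproduce.

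**Can an undosed infant arise?** Yes, under the plan's own rules.
- Inclusion precedes dosing (2.4).
- MRI confirmation may come as late as day 7 after presentation (3.2), and dosing must be done by the end of the first week from symptom onset (4.1). An infant confirmed late can be validly included with little time left.
- An infant can be withdrawn between consent and dosing (6.4).

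**Inputs for the size.** Let u be the number included but undosed, and x the number of infants with a treatment-related SAE. The documents give neither. I assume u = 0 to 3 and x = 1. That an undosed infant counts in the denominator is the usual meaning of intention to treat; the plan does not spell it out.

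**Case A: 10 included, undosed infants not replaced.** Intention to treat gives x/10; the treated percentage is x/(10 − u). The first equals the second multiplied by (10 − u)/10.

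| u | Intention to treat | Treated infants | Relative understatement |
|---|---|---|---|
| 0 | 1/10 = 10.0% | 1/10 = 10.0% | none |
| 1 | 1/10 = 10.0% | 1/9 = 11.1% | 10% |
| 2 | 1/10 = 10.0% | 1/8 = 12.5% | 20% |
| 3 | 1/10 = 10.0% | 1/7 = 14.3% | 30% |

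**Case B: undosed infants replaced until 10 are treated, as section 2.2 implies.** Intention to treat gives x/(10 + u); the treated percentage is x/10.
- u = 1: 1/11 = 9.1% against 10%.
- u = 2: 1/12 = 8.3% against 10%.

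Replacement therefore does not remove the dilution; only the choice of denominator does.

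**Case C: SAEs of any cause.** Suppose u = 1 without replacement, the undosed infant has an SAE and none of the 9 dosed infants does. Intention to treat gives 1/10 = 10%; the treated figure is 0/9 = 0%. Here the error runs the other way.

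**Scale against imprecision.** The exact two-sided 95% interval is 0.3% to 44.5% for 1/10 and 0.3% to 52.7% for 1/8. Chapter 8 plans no interval; these are given for scale only. The differences of 1.1 to 4.3 percentage points in Case A are small beside them.

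**The case against.** The strongest reply is that the plan expects every included infant to be treated. Chapter 8 describes the 10 that way, section 2.2 makes treatment of all 10 a condition for ending the study, and section 3.4 expects minimal dropout. If all are dosed, the point has no numerical effect. That stands. However, the reasons given for low dropout (PAIS is not life-threatening, follow-up is well organised) bear on loss after treatment rather than on failure to dose.

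Other parts of the safety assessment are largely unaffected, and that also stands. The stopping rules in section 6.7 count patients and concern events after, or possibly related to, MSCs. The Wilcoxon tests in section 8.1 pair a baseline value with one 24 hours after MSCs, so an undosed infant drops out. With about 10 infants described qualitatively, an attentive reader would probably see how many were treated.

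A reader might infer from section 6.5 that replacement is forbidden, so that the study could close with, say, 8 exposed infants and report 0/10. The documents do not support this: the entry states no rule, and section 2.2 points to 10 treated infants. A reader might also infer that every SAE percentage is biased downwards. That is certain only for treatment-related events, as Case C shows.

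**Conclusion.** The point holds as a modest correction to a stated rule. Section 3.4 names intention to treat as the only analysis basis and applies it to SAEs, and nothing in chapter 8 overrides it with a treated set. For treatment-related SAEs, any undosed infant lowers the reported percentage, and never raises it.

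The size depends on an assumed number of undosed infants: no effect with none; 1.1, 2.5 or 4.3 percentage points for one event with 1, 2 or 3 undosed of 10; 0.9 or 1.7 points (10% less 9.1% or 8.3%) if one or two are replaced. It would not by itself change the study's conclusion. The correction is still worth making, because it costs little and settles the denominator before any event is known.

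Sections 6.5 and 2.2 leave open what happens after a withdrawal before dosing. That is an ambiguity to reconcile, not proof of a no-replacement policy.

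**What to change.** 1. In section 3.4, replace intention to treat for safety outcomes with a set defined as all infants who received any amount of MSCs.
2. In section 8.1, state that this set is the denominator for every safety percentage.
3. List infants included but not dosed separately, each with the reason and any SAE, and report them under feasibility.
4. Delete the sentence in section 3.4 about comparing SAEs, since there is no comparator.
5. Reconcile section 6.5 with section 2.2 by stating whether an infant withdrawn before receiving any MSCs is replaced.

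The cost is wording in sections 3.4, 6.5 and 8.1, possibly one or two further consents if replacement is adopted, and a slightly less favourable treatment-related percentage if an infant goes undosed and a related event occurs.

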Animal models of neonatal brain injury provide evidence for the feasibility and efficacy of intranasal mesenchymal stromal cell (MSC) application in the treatment of PAIS. Additionally, results from human trials with MSCs in the treatment of adult stroke or other pathologic conditions provide evidence that MSC treatment is safe. This project aims at making the first step towards clinical application of MSCs to treat PAIS. Successful completion of this project will provide the first evidence of the safety and feasibility of MSCs to treat brain damage in newborn infants.

Objective: This study will assess safety and feasibility of bone marrow-derived allogeneic MSCs, administered by the nasal route, in neonates who suffered from PAIS.

Study design: A phase I/II, open-label, single-arm, single-center intervention study in the NICU at the Wilhelmina children's Hospital / University Medical Centre in Utrecht of (near-)term newborns ≥36 weeks of gestation within the first week of onset of presenting clinical symptoms.

Study population: All (near-)term newborns ≥36 weeks of gestation with or without clinical symptoms of PAIS but with a magnetic resonance imaging (MRI) confirmed PAIS (in the MCA region) will be eligible for this study. Following written parental consent, 10 patients will be included in our study.

Intervention: One dose of 50x10⁶ MSCs via the nasal route as soon as possible after confirmation of the MCA-stroke, but within the first week of onset of presenting clinical symptoms. Within 30 minutes after cleaning the nose with saline, using standard procedures operative at the NICU, the MSC will be delivered.

Main study parameters/endpoints: Our primary objective is to determine if MSC treatment in neonates with PAIS is safe in the acute setting, including vital signs at time of treatment, blood sampling before and after MSC treatment and occurrence of any adverse events.

Secondly we will investigate subacute and long-term safety of MSC treatment at 3 months, in terms of SAEs (such as infections) and cerebral tumorigenicity on MRI. Follow-up assessment at 3 months is part of regular care for neonates with PAIS.

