In summary, based on the available evidence there seems to be a solid basis for clinical translation. Animal models of neonatal brain injury provide evidence for the feasibility, efficacy and safety of intranasal MSC application in the treatment of PAIS. Additionally, results from human trials with MSCs in the treatment of adult stroke or other pathologic conditions, including BPD in neonates, provide evidence that MSC treatment is safe. This project aims at making the first step towards clinical application of MSCs to treat PAIS. Successful completion of this project will provide the first evidence of safety of MSCs to treat brain damage in newborn infants.

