6. METHODS

6.1 Study parameters/endpoints

6.1.1 Main study parameter/endpoint

Safety is defined primarily as the absence of treatment-related serious adverse events (SAEs) according to the Consolidated Standards of Reporting Trials (chapter 7.2 and bron), secondly as the absence of dose-limiting toxicity, defined as death within 24 hours after MSC transplantation or anaphylactic shock related to the MSC administration, and thirdly as the absence of adverse events at 3 months of age in terms of cerebral damage and neurodevelopmental outcome (see secondary outcome).

For acute safety, all patients will be regularly and intensively assessed, including blood sampling and vital signs, before and 24 hours after treatment, until discharge from our hospital. Also, blood sampling will be performed before and 24 hours after treatment with MSCs to determine inflammation parameters. Acute safety will be determined until discharge.

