7.4 Follow-up of adverse events

All AEs will be followed until they have abated, or until a stable situation has been reached. Depending on the event, follow up may require additional tests or medical procedures as indicated, and/or referral to the general physician or a medical specialist. SAEs need to be reported until discharge after the second MRI around the age of 3 months. As described in chapter 7 of the IB, MSCs do not survive for a very long period. When MSCs disappear within a short time frame and they are no longer present in the subject, they are not able/unlikely to lead to (serious) adverse events such as death, tumor formation or disturbances of the immune system. We have therefore decided that after a period of 3 months, AE or SAEs are very unlikely to be linked to the use of MSCs and conclusions regarding safety of MSCs can be drawn.

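### Section 3.4 announces an SAE comparison that this single-arm plan does not contain, and section 8.1 reports SAEs without an interval, although 0/10 treatment-related SAEs would leave true rates up to 30.8% open (exact two-sided 95%)

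*Combined protocol and SAP*

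**What the plan says.** The Data analysis paragraph at the end of section 3.4 states: "SAEs are planned to be compared. Statistical analysis is described in detail in chapter 8".

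The Summary describes "A phase I/II, open-label, single-arm, single-center intervention study in the NICU", and chapter 8 opens in the same terms: "This is a phase I/II, open-label, single-arm, single-center intervention study". Section 6.2 marks randomisation, blinding and allocation as not applicable.

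Section 8.1 contains one statistical test: "vital signs and blood sample parameters (continuous variables) at baseline and at 24 hours following MSC transplantation will be compared using Wilcoxon signed-rank tests". It then says that the occurrence of SAEs "will be expressed in percentages and analyzed qualitatively". Section 8.2 adds nothing.

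The endpoint definition in section 6.1.1 begins "Safety is defined primarily as the absence of treatment-related serious adverse events (SAEs". It goes on to list dose-limiting toxicity second and adverse events at 3 months third. Section 8.1 repeats all three parts; section 1 gives the first two.

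**The concern.** There are two linked problems.

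First, an analyst who reads section 3.4 expects to find an SAE comparison in chapter 8 and does not. The only comparison there is within infant, on continuous vital signs and blood values, before and 24 hours after dosing. SAEs are not part of it. No control group exists, and no historical or published SAE rate is nominated as a reference.

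Second, the leading component of the safety definition is the absence of an event, and the planned summary is a percentage. If no infant has a treatment-related SAE, the result would be reported as 0%, with nothing to show how little 10 infants can rule out. The Introduction says: "Successful completion of this project will provide the first evidence of safety of MSCs to treat brain damage in newborn infants". Section 11.1(i) adds that the trial will assess only safety in terms of (S)AEs, not therapeutic effect. Later readers will therefore lean on this one figure, and the precision of the figure is what the plan leaves out.

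An undefined comparison also leaves room to choose a reference after the SAE count is known.

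**Working it through.** **Inputs.** N = 10 treated infants, one arm (sections 3.4 and 8). Safety defined first by the absence of treatment-related SAEs (sections 1, 6.1.1 and 8.1). SAE summary: percentages and qualitative review (section 8.1). Confidence level: none is given in the documents; two-sided 95% is assumed below and alternatives are shown.

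**The plan's own figure.** Section 3.4 supports N = 10 by recruitment: 180,000 / 2300 = 78.3 PAIS cases a year, against the stated figure of about 80. With 26% involving the main MCA branch, 80 × 0.26 = 20.8 a year. Ten infants would be 10 / 20.8 = 48% of one year's pool, or 10 / 41.6 = 24% of two years'. The recruitment arithmetic reproduces. The section gives no SAE rate, margin or error level, so N = 10 cannot be traced to a precision target.

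**Is there an SAE comparison?** Setting the sections side by side:

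| Place | SAE analysis | Comparator |
|---|---|---|
| 3.4, Data analysis | to be compared; detail deferred to chapter 8 | none named |
| 6.2 | – | allocation not applicable |
| 8 | – | single arm |
| 8.1 | percentages, qualitative review | none; the paired Wilcoxon test covers continuous variables only |

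The historical case-matched controls mentioned in section 11.1(e) belong to a cited trial in preterm infants with BPD. They are not adopted here as a reference.

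**What 0/10 can exclude.** With zero events the exact (Clopper-Pearson) upper limit is 1 − a^(1/n), where a is the upper-tail probability.

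- Two-sided 95%: 1 − 0.025^(1/10) = 0.3085, i.e. 30.8%.
- One-sided 95% (equal to two-sided 90%): 1 − 0.05^(1/10) = 0.2589, i.e. 25.9%.
- Two-sided 80%: 1 − 0.10^(1/10) = 0.2057, i.e. 20.6%.

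**If events occur** (exact two-sided 95%): 1/10 gives 0.3% to 44.5%; 2/10 gives 2.5% to 55.6%.

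**How often 0/10 would be seen.** With an assumed true treatment-related SAE rate p, the chance of no events is (1 − p)^10:

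| p | Probability of 0/10 |
|---|---|
| 5% | 0.95^10 = 59.9% |
| 10% | 0.90^10 = 34.9% |
| 20% | 0.80^10 = 10.7% |
| 30% | 0.70^10 = 2.8% |

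The rates p are illustrative, since the documents give none. A true rate of one in ten would still yield a clean result in about a third of such trials.

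**The case against.** The best defence is that section 3.4 hands the detail to chapter 8, and section 8.1 gives an SAE analysis that can be carried out as written. On that reading the comparison is a stray clause in a sample-size section and no analysis is missing. This is a 10-infant pilot with no hypothesis and no threshold rate, so percentages with case review are a legitimate choice, and anyone can compute an interval from n/10. Much of this stands. The comparison is undefined rather than impossible, since an external reference may have been meant. Nor is N = 10 in dispute. What does not fall away is that two current sections disagree about what will be done with SAEs. An exact interval is itself descriptive and sits comfortably in a pilot.

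Three stronger readings are tempting, and the documents do not support them.

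- A reader might infer that 0/10 will be declared safe. No section says so. Safety has two further parts in sections 6.1.1 and 8.1, and sections 5.4, 9.4 and 11 acknowledge that risks may be unknown or unexpected in a first intranasal study in humans.
- A reader might take the remark in section 7.4 that "conclusions regarding safety of MSCs can be drawn" as licence to conclude safety from zero events. In context it justifies the length of follow-up: the cells do not persist, so events after 3 months are thought unlikely to be linked to them. It concerns when safety is judged, not how many events are acceptable.
- A reader might apply the 0/10 scenario to all SAEs. The definition concerns treatment-related ones. Section 7.2.2 counts prolonged hospital stay and persistent disability as serious, and the Introduction reports abnormal outcome or epilepsy in 50–75% of infants with neonatal stroke. Zero SAEs of any cause is therefore not the natural case.

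**Conclusion.** The point holds, at the level of wording and reporting. Section 3.4 plans an SAE comparison for which neither chapter 8 nor the design supplies a comparator. Independently, zero treatment-related SAEs in 10 infants would meet the leading part of the safety definition while true rates up to 30.8% remain compatible with the data.

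That figure assumes all 10 infants are treated and evaluable, an exact method, and a two-sided 95% level that is the reviewer's convention. One-sided 95% gives 25.9% and two-sided 80% gives 20.6%; at any of these levels a rate of one in five is not excluded. The limit reflects sampling uncertainty only, not the difficulty of attributing an SAE to treatment without a control group.

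Study conduct and the stopping rules in section 6.7 do not depend on the comparison or on an interval, so they are unaffected. What changes is the strength of the safety statement that the trial can support.

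**What to change.** 1. In section 3.4, delete the sentence that plans to compare SAEs. If an external reference was intended, name the source and its SAE rate there and in section 8.1 before any outcome data are seen.
2. In section 8.1, report treatment-related SAEs and, separately, all SAEs as n/N treated infants, each with an exact (Clopper-Pearson) 95% interval, alongside the qualitative review. Add a sentence such as: zero treatment-related SAEs in 10 infants does not exclude a true rate of up to about 31% (exact two-sided 95% limit).

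The cost is a few sentences in two sections and a slightly less favourable safety statement. If an external reference was meant, its rate has to be found and fixed in advance. No extra infants, visits or trial data are needed.
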